11.1 Sample size

Pilot / Feasibility study

30

This is a realistic number we can expect to recruit (15-20 in each study arm) over the course of 24-48months as a feasibility study.

11.2 Method of analysis

Qualitative analysis with thematic analysis. Some numerical analysis of formalised questionnaires, although statistical analysis will not be relevant will small numbers proposed.

12. Ethics

We do not anticipate any complex ethical, legal or management issues arising from the study at present. We are not proposing a deviation away from our current standard of care, but an additional therapy to be offered to patients enrolled in the intervention arm of the study.

Informed consent: patients will be given the opportunity to enrol in the study at the initial appointment but will be given the option to return 24hrs to one week later if they wish to enrol later.

Recruitment:

- We have necessary and exclusion criteria, one of which being requirement of use of a translator. The initial appointment and consenting for the study will involve a lot of information verbally, and translating questionnaires and patient information leaflets will not be an option for us.

Burdens foreseen:

- It is likely that explanation of the research, and how to use a clitoral vibrator, will require some additional time investment during the clinic although again we do not predict that this will have a negative impact on the quality of service offered in the clinic.
- The burden to the patient we feel will be minimal, with the offer of enrolment into the study on the day of clinic this will potentially avoid unnecessary visits. The follow up questionnaire will be via phone interview so further visits will be avoided.

Benefits foreseen:

- Patients will not receive monetary compensation but if in intervention group will receive a clitoral vibrator as part of the study which they will be able to keep

Other impacts:

Patients in our clinic sometimes find discussions embarrassing as we discuss sexual difficulties. This is not confined to patients in the study. We aim to minimise embarrassment and difficulties discussing sensitive topics by providing a questionnaire at baseline, and a follow up phone call rather than face to face interview is also likely to help reduce embarrassment. If the pilot study suggests that patients would prefer a different form of communication then this will feed into any further research.

Conflict of interest:

- None foreseen. None of the investigators are receiving any personal monetary grant or fund from study funders.

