	
Exclusion:
 
Any vulval skin dermatoses excluding medical management of vaginismus
 
Transgender male / on testosterone therapy
 
Symptoms of genital herpes episode in preceding 3 months
 
Unable to speak/ understand English or needing an interpreter
 
Declines to be enrolled in research study
 
Pregnancy

Statistical methodology and analysis (if applicable)	n/a
Study duration	Up to 48 months

5. Introduction

VITA DIVA- Vibration Therapy And Dilators for Vaginismus

Vaginismus results from the involuntary spasm of the pelvic floor muscles which surround the vaginal wall. This can make sexual intercourse uncomfortable, painful, or impossible, with resultant impacts on a woman's sexual pleasure and ability to conceive. There is often overlap with vulvodynia (also termed vestibulodynia), chronic vulvar pain of at least three months duration. Various clinical definitions have been proposed for vulvodynia or vestibulitis.

Successful treatment for both vulvodynia and vaginismus relies often on both medical and psychosocial interventions alongside self-help and practice. Current medical therapy for vaginismus often consists of the use of topical local anaesthetic gel, sometimes in addition to oral medications such as low dose Tricyclic Antidepressants together with recommendation of progressive vaginal dilator therapy (often termed systemic desensitisation) and physiotherapy. The fact there is not a clearly culpable etiology (and indeed causes are likely to be multifactorial) means that there is no 'gold standard' treatment for vaginismus and vulvodynia (Zolnoun, 2008). A multi-modal approach is recommended.

Anecdotally, some women find that clitoral stimulation can sometimes have a positive impact on the ability to progress with vaginal dilator treatment and general enjoyment of sexual intimacy, but this has not yet been evaluated in a research setting.

Background

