6.2 Secondary objective

Does the use of clitoral/ vulval vibrators help women to progress more easily with the use of vaginal dilators compared to women not using these? Is there any self-reported difference in experiences of pleasure or enjoyment around sexual experiences in the two groups of women as reported by FSDS and FISI Scores? Do more women report enjoyable sex? Are there any differences noted in reported ability to have or enjoyment of penetrative sexual intercourse?

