7.2 Exclusion criteria

- Unwilling or unable to give consent
- Transgender male / on testosterone therapy
- Inability to understand written and / or verbal English
- Current dermatological skin conditions requiring active treatment
- Genital herpes simplex virus symptoms within preceding 3 months
- Not reporting symptoms of vaginismus, and no evidence of vaginismus on clinical examination.

Pregnancy – via history from patient.

8. Study design

This study is a feasibility and acceptability study. The collection of qualitative data collection will be questionnaires, and interviews as described below. The data obtained will be analysed using thematic analysis to identify topics and patterns. In addition two formal, validated questionnaires will be used that can be scored to assess any change in sexual function and/or sexual distress.

Group 1 (Standard treatment)

We aim to recruit an initial 10-15 participants who will receive standard therapy with vaginal dilators and current medical management which usually consists of some or all of lidocaine gel (topical local anaesthetic applied to the vulva), tricyclic antidepressants (used in co-existing vulvodynia or vulval pain syndromes) and physiotherapy. Standard treatment also includes Group or individual psychotherapy.

Group 2 (Intervention)

In addition the standard treatment outlined above, the next 10-15 recruited will receive dilators and an external vibrator. This will take place over 6-24 months in a joint psychosexual clinic which is led by a medical doctor and a clinical psychologist.

Both groups:

Trial information will be given at the initial appointment. If the patient wishes to enrol, than an initial baseline questionnaire will be given for a patient to fill out after the clinic. A private space will be provided for the patient to do this, and there will be an offer for the patient to return to do this if preferred. Two formal, validated questionnaires will be carried out at baseline and follow up. These are the Female Sexual Distress Scale - R (FSDS) and the Female Sexual Function Index.

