Patients the Female Sexual Wellbeing clinic sometimes find discussions embarrassing as we discuss sexual difficulties. This is not confined to patients in the study. We aim to minimise embarrassment and difficulties discussing sensitive topics by providing a questionnaire at baseline, and a follow up phone call rather than face to face interview is also likely to help reduce embarrassment. If the pilot study suggests that patients would prefer a different form of communication then this will feed into any further research. Financial loss for participants is not expected.

The clitoral vibrators supplied to the patients in the intervention group are already available for sale to people in the UK. No published long term side effects from the use of these are known or foreseen.

Rubin et al published a clinical reference guide on sexual devices for clinicians in 2019 which stated that risks associated with sexual devices (such as vibrators) were traumatic injury or infection. Since we are recommending use of the vibrator for external use only, barrier use over sexual devices if shared, and proper disinfection to reduce risk of infection (Rubin, 2019).

In the unexpected case of an SAE this will be reported via the appropriate routes and the study management group will decide on whether the study should proceed or not. Participants will have an email address to contact the CI in case of AE or SAE.

No risks to researchers foreseen.

11. Statistical considerations

Qualitative study N/a

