16.3 Tools

Two formal, validated questionnaires will be used at baseline and at follow up in the study participants to assess response to treatment and intervention; the Female Sexual Distress Scale and the Female Sexual Function Index.

The Female Sexual Distress Scale (FSDS) (Derogatis, 2002) measures sexually related personal distress in women. The reliability and validity of the scale was assessed in sexually functional and dysfunctional women in three studies of approximately 500 women. The revised version contains 13 questions. It has been used to assess treatment response.

The FSDS-R measures patient-reported outcomes covering different aspects of sexual activity-related distress in women. Responses are scored from never (0) to always (4) and results in a total score of 0 to 52. Higher scores therefore equate to a higher reported level of sexual distress.

The FSDS-R had considerable scale reliability – Cronback's alpha values ranged from $\alpha=0.87$ to $\alpha=0.93$ and good test-retest reliability (intraclass correlation coefficient from $r=0.74$ to $r=0.86$. A cutoff score >11 was shown to be effective in differentiating women with and without Female Sexual Dysfunction.

The Female Sexual Function Index is another questionnaire which is widely used in the evaluation of female sexual dysfunction, assessing six main areas: desire, subjective arousal, lubrication, orgasm, satisfaction, and pain (Rosen, 2006). Higher scores equate to better sexual function. A score under 26.55 relates to low sexual function, with an individual score under 3.6 signifies low function in that area (Wiegel, 2005).

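### Section 6.2 asks between-group questions and 6.3 takes acceptability from questionnaires, yet 11.2 plans no measure of uncertainty for either on its plain reading

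*Protocol*

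**What the plan says.** **What is asked.** Section 6.2 asks whether vibrators "help women to progress more easily with the use of vaginal dilators compared to women not using these" and whether experiences differ "in the two groups of women as reported by FSDS and FISI Scores". FISI is read here as FSFI, the scale named in sections 8, 9 and 16.3. It also asks whether more women report enjoyable sex and whether ability to have, or enjoyment of, intercourse differs. Section 6.3 assesses the primary outcome, acceptability, from the baseline and follow-up questionnaires.

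**What is collected.** Section 8 says that "validated questionnaires will be used that can be scored to assess any change in sexual function and/or sexual distress". Section 16.3 gives their purpose as "to assess response to treatment and intervention". Section 5.2 lists baseline characteristics gathered so that the two groups can be compared. Section 8 states a four-point agreement scale.

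**How the groups are formed.** Sections 5 and 9 describe a non-randomised design, with controls recruited first and the vibrator group afterwards. Follow-up is by telephone at 6-24 months (section 8).

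**What analysis is planned.** The statistical methodology row of the section 4 synopsis is marked n/a. Section 11 reads "Qualitative study N/a". Section 11.2 plans thematic analysis and adds: "Some numerical analysis of formalised questionnaires, although statistical analysis will not be relevant will small numbers proposed".

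**The concern.** The objectives and the analysis section do not fit together. A study with a control group, two scored scales measured before and after, and baseline data gathered for comparing groups is not purely qualitative, yet sections 4 and 11 treat it so. The reason in 11.2, small numbers, supports leaving out hypothesis tests. It does not support leaving out precision, which matters more as groups get smaller.

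At stake is how the results can be read. A score difference or an acceptability percentage from about 15 women, given alone, does not show how many other values fit the data. For the 6.2 questions, the reader could not see that an apparent benefit is compatible with no difference. For acceptability, which is the purpose of the study, the reader could not see whether a high percentage excludes a figure near one half.

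**Working it through.** **No figure to reproduce.** The total of 30 (sections 4 and 11.1) rests on expected recruitment. The protocol gives no SD, effect size, significance level or power. Only the sum 2 x 15 = 30 can be checked, and it agrees. Differences are therefore expressed in SD units, and the 95% level is an assumption.

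**Group sizes.** 15/15 from section 5; 10/15 from section 9 (10-15 controls, then 15); 10/10 as the lower end of section 8. Section 11.1 says "This is a realistic number we can expect to recruit (15-20 in each study arm", which implies 30 to 40 in all. Because 20/20 exceeds the stated total of 30, it is not used.

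**Step 1. Difference in means, unadjusted.** Half-width = t(0.975, n1+n2-2) x sqrt(1/n1 + 1/n2).

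| Groups | t | sqrt term | Half-width (SD) | 95% CI around an observed 0.5 SD |
|---|---|---|---|---|
| 15/15 | 2.048 | 0.365 | 0.75 | -0.25 to 1.25 |
| 10/15 | 2.069 | 0.408 | 0.84 | -0.34 to 1.34 |
| 10/10 | 2.101 | 0.447 | 0.94 | -0.44 to 1.44 |

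Zero lies inside the interval at every size.

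**Step 2. Chance alone.** If there is no true difference, the probability of a gap of at least 0.5 SD favouring the vibrator group is 1 - Phi(0.5 / sqrt(1/n1 + 1/n2)), by normal approximation. This gives about 9% at 15/15, 11% at 10/15 and 13% at 10/10.

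**Step 3. Adjusting for baseline.** Half-width = t(0.975, n1+n2-3) x sqrt((1-r^2)(1/n1 + 1/n2)), with balanced baselines. The protocol gives no baseline to follow-up correlation r, so 0.5 and 0.7 are assumed.

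| Groups | r = 0.5 | r = 0.7 |
|---|---|---|
| 15/15 | 0.65 | 0.54 |
| 10/15 | 0.73 | 0.60 |
| 10/10 | 0.82 | 0.67 |

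Adjustment helps, but a 0.5 SD difference still includes zero in every cell. Sequential recruitment does not secure balanced baselines, and loss to follow-up would widen all of these.

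**Step 4. Acceptability.** For illustration, take the 83% from the vulvodynia study cited in section 5: 0.83 x 15 = 12.45, so 12 of 15 (80%). The exact (Clopper-Pearson) limits are the 0.025 quantile of Beta(12, 4) and the 0.975 quantile of Beta(13, 3), that is 52% to 96%. With 10 women in the intervention group, 8/10 gives 44% to 97%.

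**The case against.** Four arguments can be made for the protocol.

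- **The words in 11.2 are loose.** They can be taken to mean no inferential testing, which is reasonable in a feasibility study. A reader might infer that the differences are certain to be reported without any measure of uncertainty, or that a statistical analysis plan with intervals would be forbidden. The protocol does not go that far: the numerical summary it allows is undefined, and SDs or intervals are not expressly barred. This stands, and limits the point to what is planned on a plain reading. It does not remove the point, because no section mentions an interval, an SD or any other measure of precision for the study's own analysis.
- **The protocol limits its own claims.** Section 13 restricts the aim to feasibility and acceptability, section 5.3 leaves efficacy to later studies, and no decision rule depends on FSDS or FSFI. This lowers the stakes of 6.2. A reader might infer that only the secondary comparison is affected. That is not supported, since 11.2 covers the whole study, including the questionnaire-based primary endpoint in 6.3.
- **Bias is the larger threat.** Sequential allocation and the 6-24 month follow-up window could distort the comparison in ways that no interval shows. This is correct, and the revised text has to say so.
- **Section 6.2 could instead be reworded as descriptive.** That would remove the mismatch there, but would leave acceptability without a measure of precision.

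A reader might also link this point to the section 22 statement that results will support recommending the therapy. That statement is not tied to FSDS or FSFI and could rest on acceptability, so it is a separate matter and carries no weight here.

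**Conclusion.** The point holds in this form: the protocol poses comparative questions on scored scales and a questionnaire-based primary question, then sets statistical analysis aside for a reason that justifies dropping tests but not intervals. This is a position the protocol takes, not a detail it defers to an analysis plan.

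The size is considerable. At the stated total of 30, a mean difference is known only to about 0.75 SD either way, and an 80% acceptability result is compatible with anything from 52% to 96%. These figures assume a 95% level, equal SDs, approximately normal scores and complete follow-up. The adjusted figures also assume r and balanced baselines. The absence of tests, or of a power calculation, is no fault in a feasibility study, and the primary aim is not invalidated.

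**What to change.** Replace the numerical-analysis sentence in section 11.2 with:

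> The proportion of the intervention group finding vibration therapy acceptable will be reported with an exact 95% CI. FSDS-R total and FSFI total at follow-up will each be compared between groups, adjusted for the same score at baseline, and reported as a difference with 95% CI. Dilator progress and other study-specific items will be summarised by group as counts and proportions, with a 95% CI for the difference in proportions for items reported as yes/no or agree/disagree. Time from baseline to follow-up will be reported by group. The between-group comparisons are exploratory, with no hypothesis test and no efficacy claim; adjustment does not remove confounding by calendar time, case mix or length of follow-up.

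Point the n/a entries in sections 4 and 11 to this text. The thematic analysis stays as it is.

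**Cost:** a protocol wording change and a few simple estimates from data already collected, with no extra patients or visits. The downside is that the intervals will be wide. They reflect sampling error only, not bias from sequential allocation or from the 6-24 month follow-up window.

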12.1 Annual Safety Reporting

The CI will send an Annual Progress Report to the REC and the sponsor using the HRA template on the anniversary of the REC “favourable opinion”.

13. Public Involvement

This is a pilot study and is aiming only to look at feasibility and acceptability. Results and feedback from this study can therefore be used to guide any further research. Findings will be disseminated via the wordpress site we currently use to provide information to patients and staff, and we will seek advice from patients in how they wish us to disseminate findings and who they feel we should reach out to with results.

14. Data handling and record keeping

14.1 Data management

Methods of data capture:

- Patient medical records
- Baseline and follow up questionnaire
- Design of data capture forms – transcription of questionnaire results onto spreadsheet for further analysis
- Transfer and storage of data in central study database on shared drive password protected.

14.2 Source data

Source Data (baseline questionnaire, follow up questionnaire) generated by study. Source documents – medical history, patient demographics (age) will be accessed only to obtain the medical history necessary for the study (diagnosis, treatments provided, patient age).

14.3 Confidentiality

Potential participants will be identified from the patients presenting to the Female Sexual Wellbeing Clinic. Identification of participants beyond this will not be needed. Information related to study participants will be kept confidential and managed in accordance with the Data Protection Act, the General Data Protection Regulation (GDPR) 2018, NHS Caldecott Principles, the UK Policy Framework for Health and Social Care Research, and the conditions of Research Ethics Committee favourable opinion.

Access to participant healthcare records and source documents will only be by treating medical team which includes CI and PI.

Anonymisation of research data will take place upon data collection.

14.4 Record Retention and Archiving

The research data will be archived for 25 years according to Barts Health NHS Trust policy.

The data will be archived in the Modern Records Facility, [name], in physical form. After this point, the records will be destroyed.

15. Laboratories

N/a

16. Interventions and tools

16.1 Devices

Vibrator for external use. Not a medical device. Carries the CE MARK and complies with Directive 2011/65/EC Restriction on Hazardous Substances.

16.2 Techniques and interventions

Patient information leaflet will be supplied, which will detail explanations of vaginismus and vulvodynia, female sexual arousal, and massage techniques useful in these conditions.

The intervention group will receive an external clitoral vibrator for home use.

16.3 Tools

Two formal, validated questionnaires will be used at baseline and at follow up in the study participants to assess response to treatment and intervention; the Female Sexual Distress Scale and the Female Sexual Function Index.

The Female Sexual Distress Scale (FSDS) (Derogatis, 2002) measures sexually related personal distress in women. The reliability and validity of the scale was assessed in sexually functional and dysfunctional women in three studies of approximately 500 women. The revised version contains 13 questions. It has been used to assess treatment response.

The FSDS-R measures patient-reported outcomes covering different aspects of sexual activity-related distress in women. Responses are scored from never (0) to always (4) and results in a total score of 0 to 52. Higher scores therefore equate to a higher reported level of sexual distress.

The FSDS-R had considerable scale reliability – Cronback's alpha values ranged from $\alpha=0.87$ to $\alpha=0.93$ and good test-retest reliability (intraclass correlation coefficient from $r=0.74$ to $r=0.86$. A cutoff score >11 was shown to be effective in differentiating women with and without Female Sexual Dysfunction.

The Female Sexual Function Index is another questionnaire which is widely used in the evaluation of female sexual dysfunction, assessing six main areas: desire, subjective arousal, lubrication, orgasm, satisfaction, and pain (Rosen, 2006). Higher scores equate to better sexual function. A score under 26.55 relates to low sexual function, with an individual score under 3.6 signifies low function in that area (Wiegel, 2005).

16.4 Medicinal product

N/a

16.5 Other biological or chemical products

N/a

17. Safety reporting

Adverse Events (AEs) and Adverse Reactions (ARs) will be recorded. Serious Adverse Events (SAEs) and Serious Adverse Reactions (SARs) will be reported to the CI as medical assessor for the sponsor and coordinating team. All unexpected SARs (SUSARs) will be reported to the JRMO and REC.

DEVICE DEFECTS, RECALLS and ALERTS

The intervention is an external vibrator which is available for sale in the UK. It is not a medical device.

17.1 Adverse Events (AEs)

An AE is any untoward medical occurrence in a participant to whom an intervention has been administered, including occurrences which are not necessarily caused by or related to that intervention. An AE can therefore be any unfavourable or unintended sign (including an abnormal laboratory finding), symptom or disease temporally associated with study activities.

In a study of the effects of genital vibration therapy in women with arousal and orgasm disorders, light-headedness, agitation, headache, facial flushing, were each reported by 4-8% of participants, with 2% reporting some genital numbness, dizziness or cramping (Guess, 2008).

